On-treatment Tumor Biopsy	For Part 2A: The on-treatment biopsy will be collected on participants treated (about 25 participants per active Arm), and then collected per Investigator preference on per active Arm) for approximately the next 105 participants treated (about 35 participants per active Arm)										
Required Post- progression Tumor Biopsy				See Section 9.8.2							
Exploratory Biomarker Assessments											See Sections 9.5, 9.8, and Table 9.8.3-1 for all required collections.
Clinical Treatment S	upplies										
Randomization	day o		nt on Cyc						orior to the first the Medical		For Part 2A, PD-L1 result required for randomization.

Protocol Amendment No.: 09 Date: 14-Mar-2023

Approved v1000 930119402 10.0

Table 2-4: On-treatment Schedule of Activities for Part 2A Arm B and Arm C, and Part 2B

		Cy	vcle 1			Сус	ele 2		Cycles 3 and Beyond		
Procedure		(28 days	s in lengt	ch)	(28 days i	in length)		(each cycle 28 days in length)	EOT ^{a,b}	Notes
	D1	D8	D15	D22	D1	D8	D15	D22	D1		
		(± 2 days)	(± 2 days)								
									X		
BMS-986249 Administration Q8W (Part 2A Arm B and Arm C, and Part 2B)	X								Every other cycle starting at C3 [eg, C3, C5, C7, etc]		BMS-986249 to be supplied by BMS.
Nivolumab Administration Q4W (Part 2A Arm B and Arm C, and Part 2B)	X				X				X		Nivolumab to be supplied by BMS.
Patient-Reported Out	comes										See Section 9.9
EORTC QLQ-C30	X				X				X	X	For C1D1, performed after randomization but prior to first dose. All other cycles collected prior to dosing.
EQ-5D-3L	X				X				X	X	For C1D1, performed after randomization but prior to first dose. All other cycles collected prior to dosing.
FACIT GP5	X	X	X	X	X	X	X	X	X	X	For C1D1, performed after randomization but prior to first dose. All other cycles collected prior to dosing.

Table 2-4: On-treatment Schedule of Activities for Part 2A Arm B and Arm C, and Part 2B

	Cycle 1				Cycle 2				Cycles 3 and Beyond		Notes
Procedure	(28 days in length)				(28 days in length)			(each cycle 28 days in length)	EOT ^{a,b}		
D1	D1	D8	D15	D22	D1	D8	D15	D22	D1		
		(± 2 days)	(± 2 days)	(± 2 days)	(± 2 days)	(± 2 days)	(± 2 days)	(± 2 days)	(± 2 days)		
PRO-CTCAE	X	X	X	X	X	X	X	X	X	X	For C1D1, performed after randomization but prior to first dose. All other cycles collected prior to dosing.

Abbreviations: ADA = anti-drug antibody; AE = adverse event; aPTT = activated partial thromboplastin time; BMS = Bristol Myers Squibb; C = cycle; CRPC = castration-resistant prostate cancer; CT = computed tomography; CXDY = Cycle X Day Y, as an example; D = day; DNA = deoxyribonucleic acid; ECG = electrocardiogram; ECOG = Eastern Cooperative Oncology Group; EORTC QLQ-C30 = European Organisation for Research and Treatment of Cancer Quality of Life Questionnaire – Core 30; EOT = end of treatment; EQ-5D-3L = European Quality of Life – 5 Dimension – 3 Level Questionnaire; FACIT GP5 = Functional Assessment of Chronic Illness Therapy General Physical item 5; HBV = hepatitis B virus; HCC = hepatocellular carcinoma; hCG = human chorionic gonadotropin; HCV = hepatitis C virus; INR = international normalized ratio; MRI = magnetic resonance imaging; PCWG3 = Prostate Cancer Working Group 3; PD-L1 = programmed death ligand-1; PE = physical examination; PK = pharmacokinetic; PRO-CTCAE = Patient-Reported Outcomes version of the Common Terminology Criteria for Adverse Events; PSA = prostate-specific antigen; PT = prothrombin time; Q4W = every 4 weeks; Q8W = every 8 weeks; Q12W = every 12 weeks; RECIST = Response Evaluation Criteria in Solid Tumors; RNA = ribonucleic acid; SAE = serious adverse event; SARS-CoV-2 = severe acute respiratory syndrome coronavirus 2; TNBC = triple-negative breast cancer; WOCBP = women of childbearing potential.

Protocol Amendment No.: 09

^a EOT is defined as the visit where the decision is made to discontinue the participant from treatment. Evaluations will be performed prior to study discharge, or for participants who are prematurely discontinued.

For participants who complete all scheduled cycles of therapy, the EOT visit will be the same as the last scheduled and completed on-treatment visit (eg, C26D1) and the start of the Safety Follow-up Period. For participants who do not complete all scheduled cycles of therapy, the EOT visit will be the most recent on-treatment visit (with all available safety and response data); it does not need to be repeated and will be considered as the start of the Safety Follow-up Period.

Vital signs will be obtained before the first 3 infusions including BMS-986249 (C1D1, C3D1, and C5D1) and then every 15 minutes (± 5 minutes) until 60 minutes after completion of the infusion; oxygen saturation to also be performed in conjunction with vital signs monitoring on these days. For all cycles after C5 and for the nivolumab monotherapy infusions, vital signs and oxygen saturation are to be taken before the infusion and at the end of infusion. If any vital sign is abnormal (based upon clinician assessment) at the final check, the participant must be observed further for a period of time, as clinically indicated.

d Serum/urine to be collected within 24 hours prior to dosing. Pregnancy test may be completed on the first day of treatment, provided the results are available before the start of study therapy. Serum or urine pregnancy test must be performed within 24 hours prior to administration of study treatment (urine pregnancy test: minimum sensitivity 25 IU/L or equivalent units of hCG).

Protocol Amendment No.: 09

Table 2-5: Follow-up Procedural Outline for All Study Parts

	Sa	fety Follow-up					
Procedure	Follow-up 1 30 Days ^a (± 7 Days)	Follow-up 2 60 Days ^a (± 7 Days)	Follow-up 3 100 Days ^a (± 7 Days)	Imaging Follow-up	Survival Follow-up	Notes	
Safety Assessments							
PE and Vital Signs	X	X	X			Includes body temperature, seated/supine blood pressure, and heart rate.	
Laboratory Tests	X	X	X			To be performed onsite/locally. Laboratory tests also as clinically indicated; PT/INR and aPTT required for HCC and CRPC participants; for all others, coagulation assessment at screening only. For details of laboratory assessments, see Section 9.4.4 and Table 9.4.4-1.	
Urinalysis			As	clinically indicated. See So	ection 9.4.4.		
Alpha-fetoprotein	X	X	Х			For participants with HCC only. To be performed onsite/locally with laboratory tests. See Section 9.4.4 and Table 9.4.4-1.	
Pregnancy Test	X	X	Х			For WOCBP, serum/urine pregnancy test is to be performed (urine pregnancy test: minimum sensitivity 25 IU/L or equivalent units of hCG). See Section 9.2.5, Section 9.4.4 and Table 9.4.4-1.	

Table 2-5: Follow-up Procedural Outline for All Study Parts

	Sa	fety Follow-up					
Procedure	30 Days ^a 60 Days ^a 100		Follow-up 3 100 Days ^a (± 7 Days)	Imaging Follow-up	Survival Follow-up	Notes	
Viral Markers	X	Х	X			For participants with HCC only. To be completed at central laboratory. For HCV-infected; HCV RNA. For HBV-infected; HBV DNA. See Section 9.4.4 and Table 9.4.4-1.	
PSA	progression or the	start of subsequ	ient systemic ca	ncer therapy, whichever of	ccurs later. PSA evaluation	n follow-up until radiographic on beyond radiographic ression should be performed as	
Adverse Event Repor	ting and Concomita	ant Medication	Assessments				
Monitor for Non-SAEs ^b	X	X	X			For all study participants, safety reporting of AEs and SAEs should take place from date of informed consent through 100 days post EOT.	
Monitor for SAEs ^b	X	X	X			For all study participants, safety reporting of AEs and SAEs should take place from date of informed consent through 100 days post EOT.	
Concomitant Medication Assessments	X	X	Х			Including antiviral therapy for HCC participants.	

Table 2-5: Follow-up Procedural Outline for All Study Parts

	Sa	fety Follow-up								
Procedure	Follow-up 1 30 Days ^a (± 7 Days)	Follow-up 2 60 Days ^a (± 7 Days)	Follow-up 3 100 Days ^a (± 7 Days)	ays ^a Imaging Follow-up Survival Follow		Notes				
Sample Collection						See Section 9.5, and Table 9.5-2 through Table 9.5-9 for the sample collection schedule.				
Efficacy Assessments										
Tumor/Response Assessments	Part 1: Tumor assessments should occur Q12W (± 7 days), starting from the date of the last on-treatment tumor assessment. Part 2A: The first tumor imaging assessment should occur 12 weeks (± 7 days) from first dose. Subsequent tumor imaging assessments should occur Q8W (±7 days) from the date of the first tumor imaging assessment until Week 52 then continue Q12W (±7 days) thereafter. For Part 2B: Tumor imaging assessments should occur Q8W starting from the first dose (±7 days) up until Week 48, and then continue Q12W (± 7 days). For participants with HCC, a triphasic CT/MRI of the liver is required. For participants with TNBC without measurable lesions outside of the breast, contrast-enhanced MRI of the breasts should be performed along with body imaging. For all study parts: The duration of the Imaging Follow-up Period will be 100 days post EOT, or until initiation of another anti-cancer treatment, or death, whichever occurs first. See Section 9.1.1.									
Brain Imaging				ld have surveillance MRI p ast can be performed if MR		Q12W or sooner if clinically Section 9.1.1.				
Other: Bone Scan	Required for participants with prostate cancer only (PCWG3 Assessment). Should occur Q8W starting from the first dose (±7 days) up until Week 48, and then continue Q12W (±7 days) until disease progression is assessed by the investigator. Others only as clinically indicated per local standards. See Section 9.1.1.									
Subsequent Treatments (Anti-cancer)	X	X	X		X					

Protocol Amendment No.: 09 Date: 14-Mar-2023

Approved v1000 930119402 10.0

Table 2-5: Follow-up Procedural Outline for All Study Parts

	Sa	fety Follow-up				
Procedure	Follow-up 1 30 Days ^a (± 7 Days)	Follow-up 2 60 Days ^a (± 7 Days)	Follow-up 3 100 Days ^a (± 7 Days)	Imaging Follow-up	Survival Follow-up	Notes
Assessment of Participant Survival Status	X	X	X		X	Participant status will be assessed by any documented clinic visit, email, or telephone contact through 100 days post EOT.
Patient-Reported Outo	comes					Patient-reported outcomes for Part 2A and 2B participants only. See Section 9.9.
EORTC QLC-C30	X	X	X			
EQ-5D-3L	X	X	Х		X	Can be collected via telephone or email during assessment of participant survival status.
FACIT GP5	X	X	X			
PRO-CTCAE	X	X	X			

Abbreviations: ADA = anti-drug antibody; AE = adverse event; aPTT = activated partial thromboplastin time; CRPC = castration-resistant prostate cancer; CT = computed tomography; DNA = deoxyribonucleic acid; EORTC QLQ-C30 = European Organisation for Research and Treatment of Cancer Quality of Life Questionnaire - Core 30; EOT = end of treatment; EQ-5D-3L = European Quality of Life - 5 Dimension - 3 Level Questionnaire; FACIT GP5 = Functional Assessment of Chronic Illness Therapy General Physical item 5; HBV = hepatitis B virus; HCC = hepatocellular carcinoma; hCG = human chorionic gonadotropin; HCV = hepatitis C virus; INR = international normalized ratio; MRI = magnetic resonance imaging; PCWG3 = Prostate Cancer Working Group 3; PE = physical examination; PRO-CTCAE = Patient-reported Outcomes version of the Common Terminology Criteria for Adverse Events; PSA = prostate-specific antigen; PT = prothrombin time; Q8W = every 8 weeks; Q12W = every 12 weeks; RNA = ribonucleic acid; SAE = serious adverse event; SARS-CoV-2 = severe acute respiratory syndrome coronavirus 2; TNBC = triple-negative breast cancer; WOCBP = women of childbearing potential.

Protocol Amendment No.: 09

^a Follow-up visits at Days 30 (±7 days), 60 (±7 days), and 100 (±7 days) should occur relative to the last dose of study treatment or date of discontinuation, whichever is later.

b Participants will be followed for all SAEs, non-serious AEs of special interest (as defined in Section 9.2), and all AEs (SAEs and non-serious AEs) associated with confirmed or suspected SARS-CoV-2 infection until resolution, the condition stabilizes, the event is otherwise explained, the event is deemed irreversible, the participant is lost to follow-up (as defined in Section 8.3), or for suspected cases, until SARS-CoV-2 infection is ruled out.

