2 SCHEDULE OF ACTIVITIES

Study assessments and procedures are shown in Table 2-1, Table 2-2, Table 2-3, Table 2-4, and Table 2-5.

In limited instances, scheduled events (including events other than safety assessments) can occur outside of the indicated timeframes but the Sponsor should first be notified.

If a participant has a delay in study treatment administration for any reason, then assessments and laboratory tests (with the exception of any tests needed to ensure participant safety) should be correspondingly delayed with the exception of tumor assessments. Tumor assessments continue per protocol schedule regardless of any treatment delay incurred.

The pharmacokinetic (PK), and safety profiles of BMS-986249 are being elucidated, modifications to the procedures (ie, reduction in PK, sampling, timing of procedures, dose schedules) currently outlined in Section 2 and Section 9 may be required. These modifications will not include the addition of new procedures and will be documented in a note to file or administrative letter.

In the event that multiple procedures are required at a single time point, the electrocardiogram (ECG) may be obtained up to 15 minutes earlier, vital signs may be obtained up to 10 minutes earlier or later, and clinical laboratory samples may be obtained up to 5 minutes earlier than the nominal time point, ensuring the PK samples can be collected on time.

 Table 2-1:
 Screening Schedule of Activities for All Study Parts

Procedure	Screening Visit (Days -30 to -1)	Notes					
Eligibility Assessments							
Informed Consent	X	Must be obtained prior to performing any screening procedures. A participant is considered enrolled only when a protocol-specific ICF is signed.					
Contact IRT	X	After the participants meet all eligibility criteria, sites will use IRT for participant number assignment. Register in IRT to obtain participant number. Subsequent visits will be registered into the IRT system for drug supply. See Section 5.1.1. If the IRT system is not available, participants will be enrolled manually. The participant number will be created in the IRT system upon availability.					
Inclusion/Exclusion Criteria	X	Must be confirmed prior to randomization/treatment assignment. See Section 6.1 and Section 6.2.					
Medical History	X	All medical history relevant to the disease under study. Include any toxicities or allergies related to previous treatments.					
Prior Cancer Therapies	X						

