BMS-986249 Administration Q3W (Part 2A Arm A Combination Therapy Phase)	X				BMS-986249 to be supplied by BMS. BMS-986249 to be administered for up to a maximum of 4 doses.					

Protocol Amendment No.: 09 Date: 14-Mar-2023

Approved v1000 930119402 10.0

Table 2-3: On Treatment - Schedule of Activities for Part 2A Arm A and Arm D Combination Therapy Phase

	Study Trea	tment Every 3 W	eeks for 4 Cycles		
Procedure	Cycle 1, 2, 3	, 4 (each cycle 21	days in length) ^{a,c}	EOT ^{b,c}	Notes
Troccaure	D1	D8	D15	EOI	Titles
		(± 2 days)	(± 2 days)		
Ipilimumab Administration Q3W (Part 2A Arm D Combination Therapy Phase)	X				Ipilimumab to be supplied by BMS. Ipilimumab to be administered for up to a maximum of 4 doses.
Nivolumab Administration Q3W (Part 2A Arm A and Arm D	X				Nivolumab to be supplied by BMS.
Combination Therapy Phase) ^c					
Patient-Reported Outcomes					See Section 9.9
EORTC QLQ-C30	X			X	For C1D1, performed after randomization but prior to first dose. All other cycles collected prior to dosing.
EQ-5D-3L	X			X	For C1D1, performed after randomization but prior to first dose. All other cycles collected prior to dosing.
FACIT GP5	Х	X	X	X	For C1D1, performed after randomization but prior to first dose. All other cycles collected prior to dosing.
PRO-CTCAE	X	X	X	X	For C1D1, performed after randomization but prior to first dose. All other cycles collected prior to dosing.

Abbreviations: ADA = anti-drug antibody; AE = adverse event; BMS = Bristol Myers Squibb; C= cycle; CT = computed tomography; CXDY = Cycle X Day Y, as an example; D = day; ECG = electrocardiogram; ECOG = Eastern Cooperative Oncology Group; EORTC QLQ-C30 = European Organisation for Research and Treatment of Cancer Quality of Life Questionnaire – Core 30; EOT = end of treatment; EQ-5D-3L = European Quality of Life – 5 Dimension – 3 Level Questionnaire; FACIT GP5 = Functional Assessment of Chronic Illness Therapy General Physical item 5; hCG = human chorionic gonadotropin; MRI = magnetic resonance imaging; PD-L1 = programmed death ligand-1; PE = physical examination; PK = pharmacokinetic; PRO-CTCAE = Patient-Reported Outcomes version of the Common Terminology Criteria for Adverse Events; Q3W = every 3 weeks; Q8W = every 8 weeks; Q12W = every 12 weeks; RECIST = Response Evaluation Criteria in Solid Tumors; SAE = serious adverse event; SARS-CoV-2 = severe acute respiratory syndrome coronavirus 2; WOCBP = women of childbearing potential.

Approved v1000 930119402 10.0

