7.5.3 Dose Delays Due To Toxicity

If an event is attributed to BMS-986249, ipilimumab, or nivolumab, alone or in combination, then all study treatments must be delayed until treatment can resume (See Section 7.5.3.1). Tumor assessments for all participants should continue per protocol even if dosing is delayed. Participants who experience the following must have all study treatment(s) withheld:

- SARS-CoV-2 infection either confirmed or suspected
- Potential DLTs, until DLT relatedness is defined
- Drug-related select AEs and laboratory abnormalities as follows:
 - Any Grade ≥ 2 non-skin AE, with the following exceptions:
 - o Grade 2 drug-related fatigue or laboratory abnormalities do not require a treatment delay
 - Dose delay for AST, ALT, or total bilirubin abnormalities in HCC participants should be managed as follows:
 - o If baseline AST, ALT, or bilirubin is within normal limits, delay dosing for Grade ≥ 2 toxicity
 - o If baseline AST, ALT, or bilirubin is within the Grade 1 toxicity range, delay dosing for Grade ≥ 3 toxicity
 - o If baseline AST, ALT, or bilirubin is within the Grade 2 toxicity range, delay dosing for a 2-fold drug-related increase in AST, ALT, or bilirubin, or for AST, ALT, or bilirubin values 8× ULN (whichever is lower).
 - Grade 3 skin AE
 - Grade 3 laboratory abnormality, with the following exceptions:
 - o Grade 3 lymphopenia does not require a dose delay
 - ≥ Grade 3 amylase or lipase abnormality that is not associated with clinical manifestations or radiographic evidence of pancreatitis does not require dose delay
 - All troponin elevations require a dose delay

 AE, laboratory abnormality, or concurrent illness that, in the judgment of the investigator, warrants delaying study treatment administration

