Participants who require a delay of study treatment should be re-evaluated weekly or more frequently if clinically indicated. For participants receiving a combination (eg, Part 1B and Part 2), if dosing is delayed, then both study treatments must be delayed together. If dosing with both study treatments is to be resumed after a delay, then both must be resumed on the same day. Criteria for participants who are required to permanently discontinue study treatments are listed in Section 8.2. In addition, all Grade 2 GI, renal, pulmonary, hepatic, and neurological AEs should be evaluated and managed per the toxicity management algorithms in Appendix 9. Participants not meeting guidelines for permanent discontinuation will be permitted to resume therapy based on the criteria specified below in Section 7.5.3.1. Participants eligible to resume study therapy will resume study therapy at the nominal treatment visit after their last received study medication dose.

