7.5.3.1 Criteria to Resume Treatment

Participants experiencing AEs not meeting criteria for permanent discontinuation as outlined in Section 8.1 may resume treatment with study medication under the following criteria:

- Participants may resume treatment with study treatment when the drug-related AE(s) resolve to Grade ≤ 1 or baseline value, with the following exceptions:
 - Participants may resume treatment in the presence of Grade 2 fatigue.
 - Participants who have not experienced a Grade 3 drug-related skin AE may resume treatment in the presence of Grade 2 skin toxicity.
 - Participants with Grade 2 uveitis, episcleritis, iritis, eye pain, or blurred vision not meeting DLT criteria (Section 8.1) must resolve to baseline prior to resuming study therapy.
- Participants who require dose delays for drug-related elevations in AST, ALT, or total bilirubin may resume treatment when laboratory values return to baseline CTCAE Grade or normal and management with corticosteroids (if needed) is complete, provided the criteria for permanent discontinuation are not met (Section 8.1).
 - For HCC participants with baseline Grade 1 AST, ALT, or total bilirubin who require dose delays for reasons other than a drug-related hepatic event may resume treatment in the presence of Grade 2 AST, ALT, or total bilirubin.
- Participants with combined Grade 2 AST/ALT **and** total bilirubin values meeting DLT criteria (Section 7.5.1) should have treatment permanently discontinued.
- Drug-related pulmonary toxicity, diarrhea, or colitis must have resolved to baseline before treatment is resumed.
- Participants with drug-related endocrinopathies adequately controlled with only physiologic hormone replacement may resume treatment. Adrenal insufficiency requires discussion with and approval from the Medical Monitor (or designee).
- Participants with SARS-CoV-2 infection (either confirmed or suspected) may resume treatment after all of the following:

- at least 10 days (20 days for severe/critical illness) have passed since symptoms first appeared or positive test result (eg, RT-PCR or viral antigen), and
- resolution of acute symptoms (including at least 24 hours has passed since last fever without fever reducing medications), and
- evaluation by the Investigator with confirmation that there are no sequelae that would place the participant at a higher risk of receiving investigational treatment, and
- consultation by the Medical Monitor.

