10.3.7 Patient-Reported Outcome Analyses

PRO analyses are described in Table 10.3.7-1.

Table 10.3.7-1: PRO - Statistical Analyses

[figure not shown]
Secondary Endpoint	Statistical Analysis Methods
To evaluate TTD in Global Health Status/QoL of the EORTC QLQ-C30 (Part 2A only)	TTD in Global Health Status/QoL and Physical Functioning will be defined as the time from randomization until a clinically meaningful decline (ie, reduction ≥10 points) from baseline in EORTC QLQ-C30 global health/quality of life subscale score and Physical Functioning Scale score. Estimates for both Global Health Status/QoL and Physical Functioning will be provided with associated 95% CIs.
To evaluate TTD in Physical Functioning Scale of the EORTC QLQ-C30 (Part 2A only)	The analysis will use all available data from randomized participants, including data collected during post-treatment follow up. Median deterioration times, hazard ratios, and 95% CIs will be calculated

Abbreviations: CI = confidence interval; EORTC = European Organisation for Research and Treatment of Cancer; PRO = patient-reported outcome; QLQ-C30 = Quality of Life Questionnaire – Core 30; QoL = quality of life; TTD = time to deterioration.

Analyses of PRO will be performed on participants who have an assessment at baseline and at least 1 post-baseline assessment.

Further exploratory analyses for Part 2A and Part 2B not specified here will be described in the Statistical Analysis Plan, which will be finalized before database lock and may be presented separately from the main clinical study report.

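### Questionnaires move with delayed doses, so after a toxicity hold that later resumes the QLQ-C30 generally follows recovery, and time to deterioration can miss or misdate a decline

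*Combined protocol and SAP*

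**What the plan says.** **Delay rule.** Section 2 covers a dose delay from any cause: "assessments and laboratory tests (with the exception of any tests needed to ensure participant safety) should be correspondingly delayed", with tumor assessments as the one further exception. Scans keep their own timetable. Patient-reported outcomes (PROs) are not named as an exception.

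**PRO timing.** Table 2-2 (Arm F, Arm D maintenance), Table 2-3 (Arm D combination phase) and Table 2-4 (Arm C, Part 2B) place QLQ-C30 and EQ-5D-3L on Day 1 of each cycle, with the note "All other cycles collected prior to dosing". Cycles last 28 days, or 21 days in Arm D's four combination cycles. FACIT GP5 and PRO-CTCAE are also taken weekly in Cycles 1-2 (Arms C and F, Part 2B) or Cycles 1-4 (Arm D).

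**Holds.** Under Section 7.5.3 the drug-related triggers for withholding treatment include "Any Grade ≥ 2 non-skin AE, with the following exceptions". Section 7.5.3.1 states: "Participants may resume treatment with study treatment when the drug-related AE(s) resolve to Grade ≤ 1 or baseline value", again with exceptions. Section 8.1 ends treatment when a delay exceeds 8 weeks from the previous dose, apart from prolonged steroid tapers and approved non-drug reasons.

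**Contact during a hold.** Section 7.5.3: "Participants who require a delay of study treatment should be re-evaluated weekly or more frequently if clinically indicated". Section 7.5.4 adds four-weekly safety and laboratory visits for delays beyond 8 weeks. Neither mentions questionnaires.

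**Endpoint.** Time to deterioration (TTD) is a Part 2A secondary endpoint (Table 4-2). Section 10.3.7 measures it from randomization to a drop of at least 10 points in global health/QoL or physical functioning, and adds: "The analysis will use all available data from randomized participants, including data collected during post-treatment follow up".

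**The concern.** Under this rule the date of a form depends on the toxicity whose impact the form is meant to record. The participant is held because of an adverse event, and the form waits until the event has settled enough for dosing. That is informative timing written into the schedule.

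It matters because Part 2A asks whether BMS-986249 plus nivolumab is better tolerated than ipilimumab plus nivolumab. TTD is a secondary measure of participants' experience, and Section 9.9.4 adopts PRO-CTCAE on the ground that clinicians underreport symptomatic events. The plan already protects scans from this problem by keeping them on calendar time.

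**Working it through.** The plan gives no power, event rate or hold rate for TTD, so there is no figure of its own to reproduce. The check is a reading of the rules followed by interval arithmetic.

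**1. Are PROs covered by the delay rule?** Yes. The rule names two exceptions, safety tests and tumor assessments, and a questionnaire is neither. Section 7.5.3 has a participant resume at the nominal visit following the last dose received, so that visit and its form move together.

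**2. What is the participant's state at the delayed form?** Generally Grade 1 or less, or baseline, since that is the condition for resuming. Listed exceptions include Grade 2 fatigue, and Grade 2 skin toxicity where there was no Grade 3 skin event.

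**3. How long is the gap?** Gap between consecutive QLQ-C30 forms = cycle length + hold, with a general ceiling of 8 × 7 = 56 days from the previous dose.

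| Arm | Planned interval | Hold | Gap | Calendar forms displaced |
|---|---|---|---|---|
| C, F | 28 days | 7 days | 28 + 7 = 35 | 1 |
| C, F | 28 days | 28 days | 28 + 28 = 56 | 1 |
| D, combination | 21 days | 7 days | 21 + 7 = 28 | 1 |
| D, combination | 21 days | 28 days | 21 + 28 = 49 | 2 |
| D, combination | 21 days | 35 days | 21 + 35 = 56 | 2 |

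A prolonged steroid taper can take the gap past 56 days.

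**4. What happens to TTD?** A deterioration is seen only on a completed form. One that starts and resolves between forms is never counted. One that persists is dated at the delayed form. At the general limit it is late by up to 56 − 28 = 28 days in Arms C and F, and by up to 56 − 21 = 35 days in Arm D's combination phase. Later data cannot recover a decline that no form recorded.

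**5. Does this bias the arm comparison?** The documents do not supply the inputs. As an illustration under assumed rates, suppose true deterioration by 24 weeks is 50% in Arm D and 35% in Arm C or F, and take HR ≈ ln(1 − p of C or F) / ln(1 − p of D):

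- nothing missed: ln(0.65)/ln(0.50) = 0.62
- 10 points missed in D, 5 in C or F: ln(0.70)/ln(0.60) = 0.70
- 15 points missed in D, 5 in C or F: ln(0.70)/ln(0.65) = 0.83
- 10 points missed in each: ln(0.75)/ln(0.60) = 0.56

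The hazard ratio moves toward 1 in the second and third cases and away from 1 in the fourth. The direction depends on how missed declines differ by arm, which is unknown.

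**The case against.** The strongest reply is that the plan catches much of what matters.

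- Section 9.9 has forms completed at the start of a visit, before the physician is seen. A participant who attends the planned Day 1 and is then held may already have completed one. This stands, although the protocol does not say whether that form counts or is postponed.
- Toxicity meeting DLT criteria generally stops treatment (Sections 7.5.1 and 8.1, exceptions in 7.5.4). PROs are then scheduled at EOT and at Days 30, 60 and 100, and TTD uses them. This stands for participants who stop. It does not help those held and resumed.
- Weekly FACIT GP5 and PRO-CTCAE in the early cycles record symptoms before the missed dose. True, but they do not feed TTD.
- TTD is secondary, the design is exploratory, and no primary result is affected. This is correct and limits the weight of the point.

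A reader might infer that held participants complete forms only after recovery, or that TTD misses treatment-caused deterioration as a whole. The provisions above rule out both.

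A reader might also infer that Arm D's burden is understated. Section 5.4.7.1 reports 55.0% Grade 3-4 treatment-related events for nivolumab plus ipilimumab in CA209067, so more holds in Arm D are plausible. But no hold rate is given, and Arm D is also sampled more densely: every 21 days rather than 28, with weekly forms for 4 × 3 = 12 weeks rather than 2 × 4 = 8.

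Longer gaps are tempting too. An Arm D participant last assessed on Day 22, stopped on Day 78 (22 + 56) and next seen 30 days later on Day 108 would have 108 − 22 = 86 days without a QLQ-C30. That needs one reading of the EOT footnotes; on the other reading a form is due when stopping is decided. Resuming on Day 64 after a Day 1 dose is 63 days, beyond the general limit unless an exception applies.

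**Conclusion.** The concern holds in a limited form. PROs are not exempt from the delay rule, so in Part 2 participants held for toxicity and later resumed, the next pre-dose QLQ-C30 generally falls after the event has settled. The gap can reach 56 days within the general limit, against 28 or 21 planned, and more under the steroid-taper exception. In Part 2A, transient deterioration in that gap can be missed, and persisting deterioration can be dated late in TTD.

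This assumes that sites apply the delay rule as written and that no form was completed at the originally planned visit. The size and direction of any between-arm bias cannot be computed from the documents, and the hazard ratios above rest on assumed rates. The point is worth acting on because the remedy is cheap, not because a large bias has been shown.

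**What to change.** 1. Add PROs to the exceptions in Section 2: QLQ-C30, EQ-5D-3L, FACIT GP5 and PRO-CTCAE stay on the nominal calendar schedule regardless of dose delay, as tumor assessments do. During a hold they are completed at the weekly re-evaluation visit that Section 7.5.3 already requires. Telephone completion should not be extended to the other three instruments, because Section 9.9 provides it only for EQ-5D-3L.
2. Change the note in Tables 2-2, 2-3 and 2-4 to *prior to dosing if dosed that day*.
3. Reconcile the EOT footnotes to those tables. They define EOT as the visit at which stopping is decided, yet for early stoppers also treat the last on-treatment visit already held as EOT. State that the EOT PROs are completed when discontinuation is decided if the last form is not current.
4. State in the statistical analysis plan how forms completed at a visit where dosing was then withheld are used in TTD.

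The cost is schedule wording, site reminders and a few extra questionnaires for held participants. Re-evaluation during a hold is already at least weekly, so no new visits are needed there.
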